1.2 Study Schema

Figure 1-1. Study Schema

* All subjects will be started on a 70 mg dose of erenumab at day 1 with provider discretion for dose optimization. Dose optimization will allow patients to remain on 70 mg, increase the dose from 70 mg to 140 mg, and if needed decrease the dose back down from 140 mg to 70 mg. It is highly recommended that all erenumab dose adjustments be completed by week 12, after which all subjects should remain on the week 12 erenumab dose for the rest of the study. Additional dose adjustments after week 12 are not recommended and must only be made if deemed medically necessary by the investigator.

** Baseline may begin on the same day as screening.

1.3 Schedule of Activities (SoA)

Table 1-1. Subject Study Visits Through Open-label Treatment Phase

PROCEDURE	Screening (up to 3 weeks before baseline) ^c	Baseline (4-5 weeks before day 1) ^c	Open-label Treatment Period (24 weeks)							Notes
			Day 1 ^e	Week 4	Week 8	Week 12	Week 16	Week 20	Week 24/ EOS	
GENERAL ASSESSMENTS										
Informed consent	X									
Inclusion and exclusion criteria	X									
Demographics	X									
Medical history	X									
Neurological medical history	X									
Gastrointestinal medical history	X									
Headache and migraine frequency medical history	X									
Migraine preventive medications review	X	X	X	X	X	X	X	X	X	At screening, a review of the subject's history of migraine preventive use (past and current) will be conducted. At subsequent visits, information will be collected regarding concomitant standard of care preventive status (ie, whether still taking and at what dose).
Prior therapies review	X									Includes all prior medications (other than prior migraine preventive medications) that were being taken/used within 120 days prior to screening through the signing of the informed consent.
Concomitant therapies review	X	X	X	X	X	X	X	X	X	
Eligibility criteria after baseline period			X							Compliance with eDiary usage will be assessed on day 1 to determine eligibility before any other day 1 assessments.
Physical measurements			X							Height/weight for BMI

Footnotes are defined on the last page of this table.

Page 1 of 3

Table 1-1. Subject Study Visits Through Open-Label Treatment Phase

PROCEDURE	Screening (up to 3 weeks before baseline) ^c	Baseline (4-5 weeks before day 1) ^c	Open-label Treatment Period (24 weeks)							Notes
			Day 1 ^e	Week 4	Week 8	Week 12	Week 16	Week 20	Week 24/ EOS	
SAFETY ASSESSMENTS										
Adverse events			X	X	X	X	X	X	X	
Serious adverse events	X	X	X	X	X	X	X	X	X	
Adverse device effects			X	X	X	X	X	X		
Product complaints			X	X	X	X	X	X		
LABORATORY ASSESSMENTS										
Urine pregnancy test (females of childbearing potential only)	X		X			X			X	Additional on-treatment pregnancy testing may be performed at the investigator's discretion if there is suspicion that a female subject is pregnant or per local laws and regulations.
CLINICAL OUTCOME ASSESSMENTS										
eDiary		Daily				Daily				
ETS			X							
GAD-7			X			X			X	
MFIQ			X			X	X	X	X	
mGI-I						X	X	X	X	To be completed by subject and clinician
MIBS-4			X			X	X	X	X	
MSSS			X			X	X	X	X	
PHQ-9	X ^d		X			X			X	
TSQM version 1.4			X			X	X	X	X	TSQM will assess satisfaction with standard of care migraine preventive medication at day 1 and only investigational product at subsequent time points.
STUDY TREATMENT										
Amgen investigational product administration ^e			X	X	X	X	X	X		

Footnotes are defined on the last page of this table.

Table 1-1. Subject Study Visits Through Open-Label Treatment Phase

PROCEDURE	Screening (up to 3 weeks before baseline) ^c	Baseline (4-5 weeks before day 1) ^c	Open-label Treatment Period (24 weeks)							Notes
			Day 1 ^e	Week 4	Week 8	Week 12	Week 16	Week 20	Week 24/ EOS	
STUDY VISITS										
Onsite visit ^a	X	X	X			X			X	
Remote visit – site staff phone call with subject ^b				X	X		X	X		

Page 3 of 3

BMI = body mass index; eDiary = electronic diary; EOS = End of Study; ETS = Expectation of Treatment Scale; GAD-7 = General Anxiety Disorder Scale;

MFIQ = Migraine Functional Impact Questionnaire; mGI-I = Migraine Global Impression Item; MIBS-4 = Migraine Interictal Burden Scale; MSSS = Migraine Symptom Severity Scale; PHQ-9 = Patient Health Questionnaire; TSQM = Treatment Satisfaction Questionnaire for Medication

^a Screening, Baseline, day 1, week 12, and week 24/EOS visits are required to take place onsite. Subjects will be provided the doses necessary to continue erenumab monthly treatment at a non-investigative site (eg, subject's home). Additional onsite visits are optional at the investigator's discretion.

^b For remote visits (ie, visits not conducted onsite), visit data will be collected by site staff via telephone or via electronic device as applicable (eg, clinical outcomes assessments).

^c Baseline may start on the same day as the screening visit.

^d Screening PHQ-9 is to assess eligibility and will be collected on a paper form. On-study PHQ-9 assessments will be collected on the subject's eDiary device.

^e All day 1 procedures must be completed before investigational product is administered.

Table 1-2. Schedule of Activities for Key Family Members

PROCEDURE	Screening (up to 3 weeks before baseline) ^a	Baseline (4-5 weeks before day 1) ^a	Open-Label Treatment Period (24 weeks)							Notes
			Day 1	Week 4	Week 8	Week 12	Week 16	Week 20	Week 24/ EOS	
GENERAL ASSESSMENTS										
Informed consent for key family members		X								Signing of informed consent can occur any time at or before the week 12 visit. Informed consent must be signed before the week 12 mGI-I is administered.
CLINICAL OUTCOMES ASSESSMENTS										
mGI-I						X	X	X	X	

EOS = End of Study; mGI-I = Migraine Global Impression Item

^a Baseline may begin on the same day as the screening visit.

Table 1-3. Optional Substudy: Schedule of Activities for Participating Subjects, Clinicians, and Key Family Members

PROCEDURE	Screening (up to 3 weeks before baseline) ^a	Baseline (4-5 weeks before day 1) ^a	Open-Label Treatment Period (24 weeks)							Notes
			Day 1	Week 4	Week 8	Week 12	Week 16	Week 20	Week 24/ EOS	
HEALTH ECONOMIC ASSESSMENTS										
Qualitative substudy informed consent		X								Written consent will be collected from subject and key family member. Signing of informed consent and participant screening can occur any time at or before the day 1 visit.
Qualitative substudy interviews (conducted by third-party interviewer) ^b			X						X	Participating subjects' clinicians will also be interviewed. Interviewers will attempt to conduct the interview as soon as possible and within 7 days after day 1 and week 24/EOS visits.

EOS = End of Study

^a Baseline may begin on the same day as the screening visit.^b Each participant (subject, clinician, and key family member) will be interviewed separately by the third-party interviewer.

2. Introduction

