All clinical outcomes assessments (COAs) detailed in the Schedule of Activities ([Table 1-1](#)) will be performed on the subject's eDiary device regardless of visit location.

The treating clinician and a key family member (if available) for each participating subject will be invited to complete an mGI-I at weeks 12, 16, 20, and 24/EOS. The key family member should be a person in the subject's life with whom s/he interacts significantly on a day-to-day basis. This person should have a deep understanding of the impact migraine has on the subject. They should also be able to provide their perspective of change in the subject's migraines over time. The person the subject chooses to nominate can be anyone such as a spouse, daughter or son, parent, sibling, or other relative or the person with whom the subject is in a de facto relationship. The key family member must sign an informed consent before completing any study-specific procedures. The same clinician and key family member of each subject should complete the mGI-I across all visits. If the clinician or key family member is unable to complete a visit, the assessment for that visit should be noted as missed.

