6.4.2 Blinding

This is an open-label study; blinding procedures are not applicable.

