
The estimand for the secondary efficacy objectives on impression of change in migraine consists of:
 
• The target population, which includes subjects with EM or CM currently on 1 standard of care migraine prevention therapy• The endpoints, which include:
• Improvement in subject global impression at week 24, as defined by subject reporting of much improved or a little improved on the mGI-I• Improvement in treating clinician's global impression at week 24, as defined by the clinician's reporting of much improved or a little improved on the mGI-I for each individual subject• Improvement in key family member's global impression at week 24, as defined by family member's reporting of much improved or a little improved on the mGI-I for each individual subject• There are 2 intercurrent events, discontinuation of IP due to lack of efficacy or adverse event, and discontinuation of IP due to other reasons. The treatment effect of interest will be assessed for all subjects who receive at least 1 dose of IP and have at least 1 post-baseline value of each respective mGI-I item. A composite strategy will be used for subjects who discontinued IP due to lack of efficacy or adverse event where they will be defined as not improved after IP discontinuation. A hypothetical strategy will be used for those subjects who discontinued IP due to other reasons with data collected after IP discontinuation censored.• The treatment, which is erenumab 70 or 140 mg every 4 weeks	

- The summary measure, which is the proportion of subjects who achieves impression of improvement at week 24.

The estimand for the secondary efficacy objective on impression of change in migraine is the proportion of subjects who achieves global impression of migraine improvement at week 24 as defined by subject, treating clinician, or family member reporting of much improved or a little improved on the mGI-I, in subjects with EM or CM who are currently on 1 standard of care migraine prevention therapy and who receive at least 1 dose of IP and have at least 1 post-baseline value of the respective mGI-I, and a composite strategy will be used for subjects who discontinued IP due to lack of efficacy or adverse event where they will be defined as not improved after IP discontinuation, while a hypothetical strategy will be used for those subjects who discontinued IP due to other reasons with data collected after IP discontinuation censored.

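### The key family member may consent as late as week 12 of open-label treatment, so the week-24 family mGI-I proportion is open to outcome-dependent rater selection that no planned analysis would show

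*Protocol*

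**What the plan says.** Protocol Table 1-2 marks family consent in the Baseline column, but its note widens the window: "Signing of informed consent can occur any time at or before the week 12 visit". The only hard limit is the next sentence: "Informed consent must be signed before the week 12 mGI-I is administered".

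Protocol Section 4.1 makes the rater optional ("a key family member (if available) for each participating subject will be invited to complete an mGI-I") and leaves the choice to the subject: "The person the subject chooses to nominate can be anyone such as a spouse, daughter or son, parent, sibling, or other relative". It asks for someone in significant daily contact who understands how migraine affects the subject. It also holds the rater constant once rating begins: "The same clinician and key family member of each subject should complete the mGI-I across all visits". No passage dates the nomination. On blinding, Protocol Section 6.4.2 says: "This is an open-label study; blinding procedures are not applicable".

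The mGI-I estimand in SAP Section 2.1, as in the Protocol, covers dosed subjects who "have at least 1 post-baseline value of each respective mGI-I item". SAP Section 6.2 defines the efficacy analysis set as all dosed subjects, with no requirement for a rating. SAP Table 9-2 models each rater's mGI-I separately on observed data, with visit, prevailing dose and baseline MMD as the only terms.

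For the qualitative substudy, Protocol Table 1-3 sets family consent at or before day 1.

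**The concern.** By the week 12 visit the subject knows how treatment has gone. A subject who is doing well may be readier to bring in a relative, or may pick one who has noticed the change. A subject who is doing badly may not bother. If so, subjects with a family rating differ from those without one on the outcome being estimated.

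The same-rater rule does not help, because it acts only from week 12 onward. The repeated-measures model does not help either. A subject with no rater contributes no family rating at any visit, and the subject's own response is not in the model. SAP Sections 8.3 and 8.4 do not mention absent raters, and the sensitivity analysis in SAP Section 9.1 concerns the primary endpoint only. By-visit denominators may show how many family ratings exist, but not whether their availability follows response or consent date.

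At stake is one of the three rater perspectives that Protocol Section 2.1 presents as a distinctive contribution of the study. A confidence interval does not reflect this kind of error.

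**Working it through.** **1. The plan's own precision figure.** SAP Table 3-2 gives a half-width of 6.5% at 60% with effective n = 216 (240 × 0.9). Check: 1.96 × √(0.6 × 0.4 / 216) = 6.5%. It reproduces.

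**2. Effect of selection.** Let p be the true proportion whose relative would report improvement. Let a and b be the probabilities of having a family rater among improved and non-improved subjects. Then

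- share with a rater = p·a + (1 − p)·b
- observed proportion = p·a / [p·a + (1 − p)·b]

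The documents give none of p, a or b. All are assumptions; p = 60% below.

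| a | b | Share with a rater | Observed | Difference (points) |
|---|---|---|---|---|
| 70% | 70% | 70% | 60.0% | 0 |
| 70% | 65% | 68% | 61.8% | +1.8 |
| 70% | 60% | 66% | 63.6% | +3.6 |
| 70% | 50% | 62% | 67.7% | +7.7 |
| 80% | 60% | 72% | 66.7% | +6.7 |
| 60% | 70% | 64% | 56.3% | −3.8 |

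Third row in full: 0.42 / (0.42 + 0.24) = 0.636. Last row: 0.36 / (0.36 + 0.28) = 0.5625, which shows that the sign is also an assumption.

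**3. If only some raters were recruited late.** Suppose early raters are unrelated to outcome and late ones have a/b = 1.4. With a = 70%, b = 0.70 × [(1 − L) + L/1.4], where L is the late share.

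| Late share L | b | Difference at p = 60% (points) |
|---|---|---|
| 10% | 68% | +0.7 |
| 25% | 65% | +1.8 |
| 50% | 60% | +3.6 |
| 100% | 50% | +7.7 |

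**4. The matching half-width.** Table 3-2 assumes that all 216 subjects are rated. If only 62% to 72% have a family rater, as in the 70/50 and 80/60 rows:

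- 216 × 0.62 ≈ 134, so 1.96 × √(0.24 / 134) = 8.3%
- 216 × 0.72 ≈ 156, so 1.96 × √(0.24 / 156) = 7.7%

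The like-for-like comparator at 60% is therefore about 7.7% to 8.3%, not 6.5%. The illustrated differences are of similar order to that half-width or smaller; none exceeds it.

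**The case against.** The strongest reply is that the documents permit late selection but do not show that it happened. The scheduled consent point is Baseline, and week 12 is only an outer limit. The note dates a signature, not a nomination, and a relative may be named early and sign late. The selection criteria in Section 4.1 concern closeness and understanding, not outcome. **This stands.** A reader might infer that the family proportion is biased upward, or that subjects sought out favourable relatives. The documents support neither: size and sign are unknown, and the bias is zero if availability is unrelated to outcome.

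A reader might also infer that agreement between subject and family is inflated. Selection could do that, but the SAP models the three ratings separately and plans no agreement analysis, so no planned result carries the error.

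A third reply is that stopping for lack of efficacy or an adverse event is counted as not improved, which could offset an upward bias. It might, but the SAP does not say whether the rule reaches a subject who never had a family rater. Its estimand requires a rating; its analysis set does not.

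Finally, enrolment was stopped at 240, so a new nomination deadline cannot act on these subjects. That is correct, and it limits the remedy to reporting. It does not remove the need for it.

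**Conclusion.** The point holds as a gap in design and reporting. An optional rater, chosen by the subject and able to consent up to week 12 of open-label treatment, leaves the week-24 family mGI-I proportion open to selection on outcome. The planned analyses would not reveal it.

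Under the assumed 70% against 60% and 70% against 50% availability at a true 60%, the shift is +3.6 and +7.7 points. It is +0.7 to +1.8 if 10% to 25% of raters were late with a ratio of 1.4, and it could be zero or negative. These figures show what the plan leaves open; they do not estimate what occurred.

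The scope is one of three rater versions of a descriptive secondary endpoint. The primary TSQM endpoint is unaffected.

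**What to change.** **Design (Protocol Table 1-2 and Section 4.1).** Have the key family member nominated, with relationship recorded, and where possible consented, by day 1 before the first dose. Nomination by day 1 with consent left open to week 12 closes the route only partly, because the nominee could still decide whether to take part once response is known.

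**For the 240 enrolled subjects, add to the SAP:**

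1. The number of subjects with a family rater, and the consent date relative to day 1. Protocol Section 5.3 requires family members to sign and date consent personally, so sites should hold the dates.
2. Family-rater availability tabulated by the subject's own mGI-I.
3. A sensitivity estimate of the week-24 family proportion limited to raters who consented by day 1, keeping all raters in the main estimate.
4. A statement of whether the not-improved rule applies to subjects who never had a family rater.

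**Cost.** A few extra tables, with no new visits. The sensitivity estimate will be less precise than the main one, and some raters who were named early but signed late will be counted as late.

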2.1 Study Rationale

Migraine is a prevalent and disabling neurological disorder, with a significant impact on the individual, family, workplace, and society. Objectives commonly assessed in registrational clinical trials **for migraine prevention** include changes in monthly migraine days (MMD) and use of acute migraine-specific medications. These parameters, however, do not fully capture the whole breadth of the impact of migraine preventive treatments on the daily lives of patients and their families, including their satisfaction with treatment.

There is interest in the migraine provider community not only for clinical outcomes data, but also associated patient-centric data (eg, treatment satisfaction and global impression of change in migraine from different perspectives such as those of patients, providers, and key family members). Health systems are also tracking patient satisfaction as a metric for quality of care delivery. These factors begin to define a new treatment paradigm for migraine management that includes both clinical and treatment-related satisfaction outcomes.

The Erenumab Treatment Satisfaction Study is a phase 4 United States (US), open-label, interventional, prospective 24-week study evaluating treatment satisfaction with erenumab as a preventive treatment in adult subjects with episodic migraine (EM) or chronic migraine (CM) currently on 1 standard of care migraine prevention therapy. The study will measure change in subject satisfaction with erenumab and subject, clinician, and key family member global impression of change in subject's migraine condition over the life of the study.

This study seeks to mirror real-world US clinical practice by providing subjects and investigators the flexibility to optimize erenumab dosing and maintain or discontinue the existing migraine prevention therapy (ie, standard of care).

The study will be the first to evaluate patient satisfaction in a real-world migraine setting using the Treatment Satisfaction Questionnaire for Medication (TSQM), a questionnaire validated in the migraine population. It will also be the first to validate the migraine Global Impression Item (mGI-I) in migraine patients, their treating clinician, and key family member. With this validation work, it will be the first study to allow the capture of information on impression of improvement in the patient's overall condition from multiple perspectives: patient, clinician, and key family member.

2.2 Background

2.2.1 Disease

Migraine is a disabling disorder characterized by primary recurrent headaches (referred to as attacks) with or without aura (ie, visual, sensory, and/or speech symptoms that occur just before or at the onset of migraine headache), lasting 4 to 72 hours (if not treated) with at least 2 of the following pain characteristics: unilateral, pulsating, moderate or severe intensity, or aggravated by routine physical activity. Migraine attacks are often accompanied by nausea, vomiting, and sensitivity to light (photophobia) and sound (phonophobia). Migraine affects more than 10% of the world's population (Robbins and Lipton, 2010), and the prevalence of migraine is approximately 11.7% in the United States, 14.6% in Canada, and 14.7% in Europe (Stovner and Andree, 2010; Lipton et al, 2007).

The patient burden and disability, as well as the societal impact, increase with higher attack frequency. For this reason, migraine is categorized in 2 major classifications, according to frequency of migraine days per month: EM is typically defined as 0 to 14 headache days per month (Katsarava et al, 2012). **According to the International Classification of Headache Disorders (ICHD)-4 interim recommendations in 2020, EM is better defined as “Headache occurring on < 15 days a month over the last 3 months, which on some days is migraine” (Goadsby & Evers, 2020). Chronic migraine is defined as 15 or more headache days per months, at least 8 of which have to be typical migraine days, with migraine prevention typically considered in individuals with ≥ 4 MMD (Headache Classification Committee of the International Headache Society, 2018). All patients suffering from migraine can be treated with acute medications, and those suffering from frequent/long-lasting attacks and/or significant disability induced by the attacks should be considered for preventive treatment (The American Headache Society Position Statement On Integrating New Migraine Treatments Into Clinical Practice, 2018; Antonaci et al, 2010; Evers et al, 2006).** Reports suggest that out of the approximately 25% of patients with migraine in need of migraine prevention, only half of them receive migraine preventive treatments (Lipton et al, 2007).

2.2.2 Amgen Investigational Product Background: Erenumab

Erenumab is a human immunoglobulin G2 monoclonal antibody that is directed against the canonical calcitonin gene-related peptide (CGRP) receptor complex and inhibits the action of CGRP.

Calcitonin gene-related peptide belongs to the calcitonin family of peptides and is expressed in both the central and peripheral nervous systems. It is prominently involved in the pathophysiology of migraine through nociceptive modulation in the trigeminovascular system (Goadsby et al, 2002; Tajti et al, 1999).

As of the date of approval of this protocol, erenumab 70 mg and 140 mg subcutaneously (SC) every 4 weeks (Q4W) or once monthly (QM) has been approved in more than 60 countries, including the US, Australia, Switzerland, and the European Union.

A detailed description of the chemistry, pharmacology, efficacy, and safety of erenumab is provided in the [Investigator's Brochure](#).

